## 1. Protocol Title

Electrical stimulation to reduce length of stay and duration of intubation in the neurosciences-intensive care unit (Neuro ICU)

# 2. Objectives

The purpose of this pilot trial is to estimate the effect of electrical stimulation (e-stim) to the bilateral quadriceps on duration of intubation, intensive care unit (ICU) and hospital length of stay, and functional recovery in the Neuro ICU in comparison to historical matched controls. The objective of this initial pilot and feasibility study to estimate the effect size to power a future full scale randomized controlled trial of this intervention and to optimize study logistics for a future full scale trial. We propose the following specific aims:

**Specific Aim 1 - Feasibility:** Determine whether at least 80% of planned treatments can be performed as described, and that there is adequate patient population meeting inclusion criteria available for study

**Specific Aim 2 - Efficacy:** Evaluate efficacy of e-stim by comparing length of ICU stay (days from admission to "intermediate level of care" ordered in Epic) and duration of intubation (days) of subjects (for those who were intubated) to that of historical controls.

**Specific Aim 3 - Exploratory:** Evaluate functional recovery (measured by modified Rankin Scale [mRS] and Extended Glasgow Outcome Scale [GOSE] at Neuro ICU discharge) of subjects compared to that of historical controls.

**Hypothesis:** We hypothesize that e-stim treatment will be feasible in the Neuro ICU and will reduce the length of hospital stay and intubation and improve functional recovery.

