## 4. Study Design

The study will be a prospective, feasibility pilot study to estimate the effect size to power a future, full scale randomized controlled trial of electrical stimulation. The information learned in the pilot will help the team optimize study logistics for a future full-scale trial. The historical controls used for comparison will be from pooled, de-identified data pulled from quality improvement databases maintained by the Neurosciences ICU group. The research team will not have access to identifiable data for the historical controls—only means from the historical controls on data such as length of stay and hospital costs.

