## Inclusion criteria

- Age ≥18 and ≤100
- Admission to the Neuro ICU for care for a neurologic illness requiring critical care
- Prognosis for prolonged ICU stay and/or prolonged intubation as evidenced by at least one pre- morbid risk factor: age ≥ 65 years, major medical co-morbidity (ex: heart failure, chronic obstructive pulmonary disease, chronic renal insufficiency, diabetes, poorly controlled hypertension, etc.), or severe acute critical illness (APACHE II >12)

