## e. Recruitment Methods

Patients admitted to the Neuro ICU will be screened for eligibility through a review of medical records in Epic by study staff, and approached for consent. Patients with prognosticated prolonged stay will be approached on day 2 to 5 of their ICU stay for enrollment. If patients have reversible exclusion criteria, such as hemodynamic instability or elevated intracranial pressures, they will be rescreened daily for potential enrollment until day 7.

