#### **Historical Controls**

The Neuro ICU administration maintains databases for the purpose of safety and quality improvement. We propose to query this existing database to identify patients cared for in the Neuro ICU during the year 2016 that possess similar demographics and illness characteristics as our inclusion criteria. The ICU quality group will abstract data for us. The research team will not have access to identifiable data for the historical controls—only means from the historical controls on data such as length of stay and hospital costs. The information will be extracted using automated means from this database and Epic to capture average length of stay and length of ventilator support for the purposes of comparison as "historical controls". We will not be performing individual chart review.

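### The intubation endpoint has no time zero and no requirement to be intubated when e-stim starts, so it mixes in durations that e-stim could not change, with a net bias of unknown direction

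*Combined protocol and SAP*

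**What the plan says.** Section 2, Specific Aim 2, defines the second efficacy outcome as "duration of intubation (days) of subjects (for those who were intubated) to that of historical controls". The companion outcome has a stated start, "length of ICU stay (days from admission to" step-down orders; the intubation outcome has none.

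Intubation at entry is not required. Section 5b asks for "Prognosis for prolonged ICU stay and/or prolonged intubation as evidenced by at least one pre- morbid risk factor", and the exclusion list does not mention intubation status. Section 5e sets the timing: "Patients with prognosticated prolonged stay will be approached on day 2 to 5 of their ICU stay for enrollment". For patients with reversible exclusions only, "they will be rescreened daily for potential enrollment until day 7".

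For the controls, Section 6 (Historical Controls) has the quality group query 2016 data "to capture average length of stay and length of ventilator support for the purposes of comparison", again with no landmark day. Section 4 says the team will receive "only means from the historical controls on data such as length of stay and hospital costs".

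Section 8 (Group Comparisons) compares the two means by t-test, with regression on covariates if needed. The covariate list includes neither intubation status at entry nor the ICU day of the first session.

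**The concern.** Take a patient intubated on admission, extubated on ICU day 1 and enrolled on day 3. This patient was intubated, so belongs to the Aim 2 comparison, yet unless re-intubated has a duration that was complete before any e-stim. Nothing in the endpoint definition, the eligibility criteria or the analysis removes or separates such patients.

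The pilot exists to supply an effect size for a full-scale randomised trial. If its intubation difference depends on how many enrolled patients were already extubated, and on how differently the two groups were selected, it is a poor planning input. A small or null difference could not be told apart from these artefacts. Requiring controls to have still been in the ICU on the enrolment day would not be enough, because patients already extubated by then would remain in both groups.

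**Working it through.** **1. The plan's own figure.** Section 8 (Power Calculation) plans for 10 versus 7 days, a difference of 3, with 80% power at 0.05 and 113 per group. No SD is given, so 113 cannot be reproduced directly. Assuming a two-sided test and a common SD, the normal formula gives

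SD = √(113 × 3² / 2) / (1.960 + 0.842) = 22.55 / 2.802 ≈ 8.05.

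(Rounding up, SD 8.02 gives 113 per group and 8.05 gives 114.) The pilot size does reproduce: 0.20 × 226 = 45.2, and 22 + 23 = 45.

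**2. Patients extubated before the first session.** Let a share p of intubated e-stim patients have a fixed mean duration a, and let the rest have mean b − 3 with e-stim and b without. Assume the same p, a and b in controls. Then

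control − e-stim = [p·a + (1 − p)·b] − [p·a + (1 − p)(b − 3)] = 3(1 − p).

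The last column is the size of a trial planned on that difference, n = 2 × 8.05² × 2.802² / d². The documents give no value for p.

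| p (assumed) | Expected difference d | n per group at SD 8.05 |
|---|---|---|
| 0 | 3.0 | 114 |
| 0.1 | 2.7 | 140 |
| 0.2 | 2.4 | 177 |
| 0.4 | 1.8 | 314 |

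**3. A bias in the other direction.** E-stim patients must still be in the ICU when enrolled; no such condition is stated for controls. An illustrative simulation assumed that all patients were intubated at ICU admission, with exponential ventilation time (mean 10 days) and an ICU stay longer than that by an exponential time averaging 1, 2 or 4 days. With no e-stim effect at all, mean intubation in the e-stim group exceeded that of controls by:

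- about 0.1 to 1.1 days for a first session 1 to 2 days after admission;
- about 1.3 to 4.9 days for a first session 4 to 6 days after admission.

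Now let e-stim shorten the remaining time by 30%, which is 3.0 days among those still intubated. With a first session at 4 days and ICU stay averaging 2 days beyond ventilation, the observed difference was 0.41 days in favour of e-stim. With 1 day beyond ventilation it was 0.22 days against e-stim. These inputs are assumptions; they show only that the sign can change.

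**4. Days before the first session that both groups share.** Suppose 4 of 10 days precede the first session and e-stim cuts the remaining 6 by 30%, to 4.2. Counted in total, the difference is 10 − 8.2 = 1.8 days. Counted from the first session, it is 6 − 4.2 = 1.8 days. The difference in days is the same, while the percentage is 18% in one case and 30% in the other. Where these days vary between patients they can also add variance.

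**The case against.** The strongest objections concern how far the point reaches.

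- A reader might infer that the estimate is simply pulled toward zero. The documents do not support that. The 3(1 − p) result needs the same early-extubation mix in controls, and step 3 shows a bias of comparable or larger size acting against e-stim. This objection stands.
- A reader might infer that duration is counted from intubation and that every day before the first session dilutes the effect. The start point is not written. The control figure is total ventilator support, so total duration is the natural reading, but it remains an inference. Days common to both groups cancel in the planned difference of means; only the percentage changes.
- Selecting patients with a prolonged prognosis should lower p. It does not make it zero, because a prognosis for long ICU stay alone suffices. Section 5f also provides for patients who consent for themselves.
- The pilot is imprecise in any case. With 22 and 23 patients all intubated and SD 8.05, the 95% half-width is about 2.02 × 8.05 × √(1/22 + 1/23) = 4.8 days, so a shift of 0.6 to 1.2 days (p = 0.2 to 0.4) lies well inside the noise. That is true, but imprecision is no reason to leave an avoidable bias in an estimate intended for planning.
- It might be said that patients not intubated at the first session carry no information. That is too strong: someone first intubated or re-intubated after e-stim starts has that episode wholly after exposure.

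**Conclusion.** The point holds as a defect of definition. Aim 2 sets neither a time origin nor an at-risk population for intubation, and applies no common landmark to the two groups. Followed as written, the plan admits durations that ended before any e-stim into an efficacy comparison meant to inform the randomised trial.

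The size is conditional. Under equal mix, a 3-day effect appears as 2.4 days at p = 0.2 and 1.8 days at p = 0.4, with p assumed. The requirement that only e-stim patients stay in the ICU until enrolment can offset or reverse a true benefit, so the net direction is not known. Enrolment as late as day 7 applies only to patients with reversible exclusions and should not be read as the general window. Aim 1 (feasibility) is unaffected.

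**What to change.** Amend Section 2 (Aim 2), Section 6 (Historical Controls) and Section 8 (Group Comparisons) as follows.

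- **Main comparison:** days from time zero to liberation, in patients still intubated at time zero. For e-stim patients, time zero is the first session. For controls, it is a matching ICU day fixed before extraction. If that day is to reflect the observed e-stim start days, such as their median, extraction has to wait until enrolment closes.
- **Control data:** ask the quality group to apply the still-intubated condition in its automated query and return the landmarked mean. This must be agreed beforehand, because means already supplied cannot be landmarked later.
- **Later intubations:** report episodes that begin after time zero separately in both groups.
- **Secondary:** keep total duration among all who were intubated.

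The cost is protocol wording and a revised query. Fewer patients will contribute to the main comparison, and a single control landmark only approximates start days that vary between e-stim patients. The query also needs intubation and extubation dates, which the documents do not confirm the database or the electronic record can supply by automated means; this should be checked first. No treatment procedure changes.

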## 3. Background

Neurosciences Intensive Care Unit (Neuro ICU) patients have a unique risk factor profile for developing ICU-associated weakness, leading to prolonged periods of intubation and prolonged lengths of stay. Neurologic impairment from the patient's underlying condition interacts synergistically with loss of strength and deconditioning from immobility in the Neuro ICU to create severe impairment. Multiple mechanisms drive muscle atrophy in Neuro ICU patients: mitochondrial dysfunction, changes in microcirculation, the release of pro-inflammatory cytokines, inactivation of sodium channels of skeletal muscles, and increases in calpain, a protein involved in skeletal muscle protein breakdown (Koukourikos 2014). This atrophy may contribute to "intensive care unit acquired weakness," along with axonal neuropathy from immobilization. The main risk factors for ICU-associated weakness include high severity of illness upon admission, sepsis, multiple organ failure, prolonged immobilization, hyperglycemia, and advanced age (Hermans 2015). Weakness is present in up to 2/3 of patients who are mechanically ventilated for a week (Ali 2008, Sharshar 2009), and 25% of these remain weak for at least another 7 days after awakening (De Jonghe 2002).

Reducing the duration of immobilization is an important target for preventing ICU-associated weakness. While early mobilization has been shown to improve functional outcomes in Neuro ICU patients and decrease length of stay (LOS), there are risks to early mobilization. Risks associated with early mobilization unique to neurologically critically ill patients include increased intracranial pressure, hemodynamic instability, vasospasm and decreased cerebral blood flow with resultant cerebral ischemia (Olkowski 2017). Further compounding these difficulties is the high incidence of neurologic dysfunction such as aphasia and delirium, rendering many patients unable to reliably follow commands. Thus, many patients cannot participate in traditional physical therapy facilitating early mobilization. Interventions that could provide some of the benefits of early mobilization without these risks would be of great utility in the Neuro ICU.

A number of studies have demonstrated that electrical stimulation of the lower extremity muscles, generally the quadriceps, can retard disuse atrophy and loss of strength associated with medical ICU stays, and one study has

shown reduced length of intubation and accelerated functional recovery. In most studies, stimulation was applied to the lower extremity muscles bilaterally, generally to the quadriceps, and occasionally also to the hamstrings and/or calves, and in one study to the biceps brachii of the upper extremities. Stimulation was applied for 30 to 60 minutes/day, between 3x/week to twice/day for up to 14 days or until ICU discharge, whichever came first, with sufficient current amplitude to produce a muscle contraction.

Recent meta-analyses support that electrical stimulation results in positive outcomes in critically ill patients. These positive outcomes include accelerated recovery of, or better preservation of, muscle strength after cardiothoracic surgery (Fischer et al. 2016) and, in one study, the weaning period was statistically significantly shorter in patients undergoing electrical stimulations as compared to the control group [1 (0 to 10) days vs. 3 (0 to 44) days, respectively, median (range), P = 0.003], and activity limitations were reduced reflected by increased 6 minute walk test distance, and the average days to achieve transfer from the bed to the chair was reduced from 14.33 days to 10.75 days (Routsi 2010, Burke et al. 2016). Similar outcomes, including increased strength, VO2 max, and 6-minute walk test distance, as well as improved mood and quality of life, have been demonstrated in response to lower extremity electrical stimulation in patients with heart failure or other advanced diseases (Gomes Neto et al. 2016, Jones et al. 2016). Sepsis, edema, and receipt of vasopressors is associated with lower likelihood of response to this intervention (Segers 2014). Overall, these studies support that electrical stimulation can improve outcomes, including reducing duration of ventilation and accelerating recovery of functional mobility, in appropriately selected critically ill patients and in those with advanced systemic disease

To date, no published trials have evaluated the impact of electrical stimulation on patients in the Neuro ICU and none have evaluated the impact specifically on length of ICU and hospital stay. We therefore propose a trial to estimate the effect of electrical stimulation (e-stim) to the bilateral quadriceps on duration of intubation, ICU and hospital length of stay, in 22 patients in the OHSU Neuro ICU and compare these outcomes with historical pooled de-identified data from the Neuro ICU quality/safety database with regards to age, sex, illness severity, comorbidities and other predictors of LOS.

## 4. Study Design

The study will be a prospective, feasibility pilot study to estimate the effect size to power a future, full scale randomized controlled trial of electrical stimulation. The information learned in the pilot will help the team optimize study logistics for a future full-scale trial. The historical controls used for comparison will be from pooled, de-identified data pulled from quality improvement databases maintained by the Neurosciences ICU group. The research team will not have access to identifiable data for the historical controls—only means from the historical controls on data such as length of stay and hospital costs.

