#### **Group Comparisons**

The study team statistician will analyze the data, and will be blinded to treatment assignment ("Group A" and "Group B", instead of "E-Stim Group" "Historical Controls"). Descriptive statistics will be used to quantify feasibility. Mean length of stay and mean duration of intubation will be compared between the e-stim group and the historical controls using a t-test. If necessary, a linear regression model for length of stay and/or intubation duration will be used to compare between groups while controlling for the potential confounding of covariates. A Wilcoxon rank-sum test will be used to compare the exploratory functional outcome measures between groups, as the mRS and GOSE are both ordinal scales.

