## **Power Calculation**

We plan a future trial to determine the efficacy of electrical stimulation to reduce days of mechanical ventilation by 30% (from 10 days to 7 days, observed in the Routsi study). Estimated sample sizes for a two-sample means test (Satterthwaite's t test) assuming unequal variances, with an 80% power to detect a 30% difference in days of mechanical ventilation with a significance level of p=0.05, would require 113 patients in each group (for a total of 226 subjects). In order to prepare for this future RCT, we propose a pilot trial of 45 subjects (20% of the full sample size), with 22 patients in the intervention group (e-stim) and 23 historical controls.

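### The team is to receive only means for the historical controls, which cannot support the t-test, adjusted regression or Wilcoxon test planned in section 8, and no source is given for control mRS/GOSE

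*Combined protocol and SAP*

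**What the plan says.** Section 4 (Study Design) limits the team to "only means from the historical controls on data such as length of stay and hospital costs", and section 6 (Historical Controls) repeats the limit. Section 6 says the 2016 data will be extracted automatically "to capture average length of stay and length of ventilator support", and adds: "We will not be performing individual chart review".

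Section 8 (Group Comparisons) plans three between-group analyses:

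- a t-test on mean length of stay and mean duration of intubation;
- if necessary, "a linear regression model for length of stay and/or intubation duration will be used to compare between groups" with adjustment for covariates;
- for mRS and GOSE, "A Wilcoxon rank-sum test will be used to compare the exploratory functional outcome measures between groups".

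Section 8 (Power Calculation) sets the pilot at 45 subjects, "with 22 patients in the intervention group (e-stim) and 23 historical controls". Its calculation for the future trial is made "assuming unequal variances, with an 80% power to detect a 30% difference in days of mechanical ventilation".

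In section 2, Aim 2 compares "duration of intubation (days) of subjects (for those who were intubated) to that of historical controls", and Aim 3 compares mRS and GOSE with the controls. Sections 6 and 7a describe those two scales only as assessed by study staff, which for enrolled subjects happens at Neuro ICU discharge.

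**The concern.** The data promised in sections 4 and 6 do not match the analyses promised in section 8. A control mean gives a raw difference in means and nothing about its precision.

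Three things are at stake.

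- **Effect size.** The pilot's stated objective is an effect size to power a later randomised trial. Without a control SD there is no unequal-variance test, no standardised effect and no control variance to carry forward.
- **Confounding.** The comparison is non-randomised, setting 2016 patients against later enrolees. The regression is the only adjustment planned, and it cannot be run without control outcomes by covariate.
- **Aim 3.** The functional comparison has no stated control data at all.

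A smaller wording point: section 2 calls the controls matched, but section 6 describes only a search for patients with similar characteristics, carried out by the quality group.

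**Working it through.** **Inputs from the documents.** 22 e-stim subjects and 23 controls; means of 10 and 7 ventilator days, a difference of 3; 113 per group, 80% power, significance level 0.05 (taken as two-sided). No SD is stated anywhere, so every SD or SD ratio below is an assumption.

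**The plan's own figure.** 113 per group cannot be reproduced directly without an SD, so I solved backwards. An unequal-variance t-test with 113 per group, a difference of 3 and 80% power implies two variances summing to about 128, or a common SD of about 8.0. The figure is plausible and is not in dispute. The pilot size also checks: 0.20 × 226 = 45.2, and 22 + 23 = 45.

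**What each planned analysis needs**

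| Analysis | Needed from controls | Provided for |
|---|---|---|
| t-test | n, mean, SD | mean; n = 23 overall, but not the number intubated |
| Adjusted regression | outcomes jointly with covariates, as rows or as n, mean and SD by stratum | outcome means only |
| Wilcoxon on mRS/GOSE | individual scores or category counts | no source stated |

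**The means do not determine the t-test.** Fix the means at 7 and 10 and the sizes at 22 and 23, and vary only a common assumed SD. The Welch p-value is <0.001 at SD 2, 0.016 at SD 4, 0.10 at SD 6, 0.22 at SD 8, 0.32 at SD 10 and 0.41 at SD 12.

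**A mean does not determine the Wilcoxon test.** Take 22 constructed e-stim mRS scores (eleven 3s, eleven 4s) against four constructed sets of 23 control scores, each with mean 4.0. The p-values are 0.0001, 0.039, 0.11 and 0.91.

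**Workaround 1: treat the control mean as a fixed constant.** If that mean comes from 23 patients, the standard error is too small by a factor √(1/22 + 1/23) / √(1/22) = 1.40. The simulated two-sided type I error is about 0.15 instead of 0.05 (normal data, equal SDs).

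**Workaround 2: let the e-stim SD stand in for the control SD.** The statistic is the difference divided by SD_e × √(1/22 + 1/23), with 21 df and critical value 2.080. Let k = control SD / e-stim SD. The true type I error is P(|t₂₁| > 2.080/f), where f = √[(1/22 + k²/23) / (1/22 + 1/23)]. At k = 10/7, for example, f = 1.228 and 2.080/1.228 = 1.693, giving 0.105.

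For the future trial, split the variance sum of about 128 by k, so that SD_e = √(128/(1 + k²)). Size the trial as if both SDs equalled SD_e, then compute power with the true pair.

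| k | Type I error (22 v 23) | Coverage of nominal 95% interval | Implied e-stim SD | n per group from substitution | True power |
|---|---|---|---|---|---|
| 0.75 | 0.029 | 97% | 9.06 | 145 | 89% |
| 1.0 | 0.050 | 95% | 8.01 | 114 | 80% |
| 1.25 | 0.080 | 92% | 7.08 | 89 | 70% |
| 10/7 = 1.43 | 0.105 | 89% | 6.50 | 75 | 62% |
| 2.0 | 0.200 | 80% | 5.06 | 46 | 43% |

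Ratio 10/7 is what results if the SD is proportional to the planned means. The 114 against 113 at k = 1 is rounding. Simulation (400,000 runs) gave the same type I errors at k = 1, 10/7 and 2.

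**The case against.** The best defence is that the limit to means is a privacy statement, contrasting with identifiable data, and that de-identified rows will in fact be supplied. Several places lean that way. Section 5a speaks of pooled, de-identified historical patients. The last paragraph of section 3 promises comparison with regard to age, sex, severity and comorbidities. Section 8 collects covariates to check comparability and blinds the statistician with Group A and Group B labels, which makes little sense if one group is a single mean. But none of these places promises rows, SDs or covariate values for controls, while the limit to means is explicit and stated twice. On this reading the sections still contradict each other and need reconciling.

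Other points stand in part:

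- The regression is conditional. Even so, it could not be run if judged necessary.
- The list of control data is introduced as examples, so other variables are not excluded. No section names them.
- Aim 3 is labelled exploratory and Aim 1 (feasibility) is untouched.
- Nobody has proposed substituting the e-stim SD. The figures show what a workaround would cost, assume normal data, and show no error at ratio 1 and a conservative one at 0.75.
- The 22 v 23 figures fit length of stay. For ventilator days the number of intubated controls is unknown.
- The unequal-variance assumption comes from the future trial's calculation. Section 8 does not say which t-test the pilot will use.
- Section 3 lists comparison variables, though no matching procedure. The matching point is minor, and the conclusion does not rest on it.

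**Conclusion.** The concern holds and must be fixed before the analysis. As written, none of the three between-group analyses in section 8 can be run as specified from the control data described in sections 4 and 6, and Aim 3 has no stated control data. This follows from the text and needs no assumption about SDs.

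The numerical consequence does need one. A t-test from means and n = 23 is valid only if the two variances are equal, and the plan's own power calculation assumes they are not. Over assumed SD ratios from 0.75 to 2.0, with normal data, interval coverage runs from about 97% down to 80%. True power of a future trial sized this way runs from about 89% down to 43%. The direction depends on which group is more variable, which the documents do not show. The raw difference in means and the feasibility aim are unaffected.

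**What to change.** Amend sections 4 and 6 so that the ICU quality group releases a de-identified file with one row per control. It should hold ICU days, ventilator days (blank if never intubated) and whichever section 8 covariates the database contains.

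If only aggregates can be released:

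- require n, mean and SD for each outcome, overall and by covariate stratum, with the number intubated for ventilator days;
- limit the adjustment in section 8 to what those strata allow;
- request counts per mRS and GOSE category, if they exist.

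If the database holds no 2016 mRS or GOSE scores, drop the Wilcoxon comparison and restate Aim 3 as a single-group description. In section 2, name the matching variables the quality group will use, or stop calling the controls matched.

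The cost is protocol and IRB wording, with no new patients and no chart review. Release of rows depends on the quality group's agreement, which the documents do not show; hence the aggregate fallback. With about 23 controls, strata will be small and adjustment limited to very few covariates.
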